6. DOSING DELAYS/DOSE MODIFICATIONS

6.1 MK-3475 Dose Modifications

6.1.1 General MK-3475 Dose Modifications

MK-3475 will be withheld for drug-related Grade 4 hematologic toxicities, non-hematological toxicity \geq Grade 3 including laboratory abnormalities, and severe or life-threatening AEs.

The table below includes general guidelines for toxicities that are not listed in the AE-specific table (see [section 6.1.2](#)).

General Dose Modification Guidelines for Drug-Related Adverse Events.

Toxicity	Grade	Hold Treatment (Y/N)	Timing for restarting treatment	Dose/Schedule for restarting treatment	Discontinue Subject
Hematological Toxicity	1, 2, 3	No	N/A	N/A	N/A
	4	Yes	Toxicity resolves to Grade 0-1 or baseline	May increase the dosing interval by 1 week	Toxicity does not resolve within 12 weeks of last infusion Permanent discontinuation should be considered for any severe or life-threatening event

Toxicity	Grade	Hold Treatment (Y/N)	Timing for restarting treatment	Dose/Schedule for restarting treatment	Discontinue Subject
Non-hematological toxicity Note: Exception to be treated similar to grade 1 toxicity 
 • Grade 2 alopecia • Grade 2 fatigue For additional information regarding Adverse Events with a potential Immune-Etiology reference Section 6.1.2.	1	No	N/A	N/A	N/A
	2	Consider withholding for persistent symptoms	Toxicity resolves to Grade 0-1 or baseline	Clinical AE resolves within 4 weeks: Same dose and schedule Clinical AE does not resolve within 4 weeks: May increase the dosing interval by 1 week for each occurrence	Toxicity does not resolve within 12 weeks of last infusion
	3	Yes	Toxicity resolves to Grade 0-1 or baseline	May increase the dosing interval by 1 week for each occurrence	Toxicity does not resolve within 12 weeks of last infusion
	4	Yes	N/A	N/A	Subject must be discontinued

In case toxicity does not resolve to Grade 0-1 within 12 weeks after last infusion, trial treatment should be discontinued. With Principal Investigator agreement, subjects with a laboratory adverse event still at Grade 2 after 12 weeks may continue treatment in the trial only if asymptomatic and controlled. Patients who experience a recurrence of the same severe or life-threatening event at the same grade or greater with re-challenge of MK-3475 should be discontinued from trial treatment.

Additionally, immune-related adverse events (irAEs), defined as adverse events of unknown etiology, associated with drug exposure and consistent with an immune phenomenon, may be predicted based on the nature of the MK-3475 compound, its mechanism of action, and reported experience with immunotherapies that have a similar mechanism of action. Special attention should be paid to AEs that may be suggestive of potential irAEs. An irAE can occur shortly after the first dose or several months after the last dose of treatment. All AEs of unknown etiology associated with drug exposure should be evaluated to determine if they are possibly immune-related. If an irAE is suspected, efforts should be made to rule out neoplastic, infectious, metabolic, toxin or other etiologic causes prior to labeling an adverse event as an irAE.

The table below includes guidelines for managing irAEs that are not listed in the AE-specific table (see [section 6.1.2](#)).

General Dose Modification Guidelines for Drug-Related Immune-Related Adverse Events

irAE	Withhold/Discontinue MK-3475?	Supportive Care
Grade 1	No action	Provide symptomatic treatment
Grade 2	May withhold MK-3475	Consider systemic corticosteroids in addition to appropriate symptomatic treatment
Grade 3 and Grade 4	Withhold MK-3475 Discontinue if unable to reduce corticosteroid dose to < 10 mg per day prednisone equivalent within 12 weeks of toxicity	Systemic corticosteroids are indicated in addition to appropriate symptomatic treatment. May utilize 1 to 2 mg/kg prednisone or equivalent per day. Steroid taper should be considered once symptoms improve to Grade 1 or less and tapered over at least 4 weeks.

6.1.2 AE-specific MK-3475 Dose Modifications and Supportive Care Guidelines

The table below includes recommendations on the management of specific AEs and when to hold and/or discontinue MK-3475. These guidelines are intended to be applied when the investigator determines the events to be treatment-related. Note: if after the evaluation the event is determined not to be related, the investigator does not need to follow the treatment guidance. Therefore, these recommendations should be seen as guidelines and the treating physician should exercise individual clinical judgment based on the patient.

Event(s)	CTCAE v5.0 Grade	Management / Next Dose for MK-3475	Action / Supportive Care Guidelines	Symptoms ^a	Differential Diagnosis

Colitis events
 
 • Bowel obstruction • Colitis • Colitis microscopic • Enterocolitis • Enterocolitis hemorrhagic • Gastrointestinal (GI) perforation • Necrotizing colitis 
Diarrhea
 
All patients who experience diarrhea should be advised to drink liberal quantities of clear fluids. If sufficient oral fluid intake is not feasible, fluid and electrolytes should be substituted via IV infusion.
	≤Grade 1	No change in dose	
 • For diarrhea, treat symptomatically (loperamide, oral hydration, electrolyte substitution and ADA colitis diet). Endoscopy is recommended if symptoms persist. • Grade 1 diarrhea that persist for >1 week should be treated with the addition of oral diphenoxylate hydrochloride and atropine sulfate four times daily and budesonide 9 mg daily. 	
Symptoms may include (but not limited to):
 
 • Abdominal pain, cramping and/or bloating • Blood and/or mucus in stool with or without fever • Constipation • Diarrhea • Ileus • Nausea and/or vomiting • Peritoneal signs consistent with bowel perforation • Rectal bleeding • With or without fever 
Patients with diarrhea should be carefully monitored for signs and symptoms of enterocolitis (such as diarrhea, abdominal pain, blood or mucus in stool, with or without fever) and of bowel perforation (such as
	
All attempts should be made to rule out other causes such as metastatic disease, bacterial or parasitic infection, viral gastroenteritis, or the first manifestation of an inflammatory bowel disease by examination for stool leukocytes, stool cultures, and a Clostridium difficile titer.

	Grade 2	
Hold until ≤Grade 1.
 
Resume at same dose level. May increase dosing interval by 1 week if it takes more than 4 weeks for toxicities to resolve.
	
 • GI consultation and endoscopy is recommended to confirm or rule out colitis for grade 2 diarrhea that persists >1 week or grade 1-2 diarrhea with rectal bleeding (additional guidelines for the treatment of persistent colitis are provided below). • Grade 2 diarrhea should be treated with the addition of oral diphenoxylate hydrochloride and atropine sulfate four times daily and budesonide 9 mg daily. • Grade 2 diarrhea with diffuse ulceration and bleeding seen on endoscopy may require oral steroids with prolonged taper and represent an increased risk for the development of bowel perforation. • When symptoms improve to grade 1 or less, steroid taper should be started and continued over no less than 4 weeks. • In patients with Grade 2 enterocolitis, MK-3475 should be withheld and anti-diarrheal treatment should be started. If symptoms are persistent for more than one week, systemic corticosteroids should be initiated (e.g., 0.5 mg/kg/day of prednisone or equivalent). When symptoms improve to Grade 1 or less, corticosteroid taper should be started and continued over at least 1 month. 		

Event(s)	CTCAE v5.0 Grade	Management / Next Dose for MK-3475	Action / Supportive Care Guidelines	Symptoms ^a	Differential Diagnosis
	Grade 3-4	
Withhold MK-3475
 
Discontinue if unable to reduce corticosteroid dose to <10 mg per day prednisone equivalent within 12 weeks of toxicity
	
 • In patients with Grade 3 enterocolitis, MK-3475 will be permanently discontinued and treatment with systemic corticosteroids should be initiated at a dose of 1 to 2 mg/kg/day of prednisone or equivalent. When symptoms improve to Grade 1 or less, corticosteroid taper should be started and continued over at least 1 month. 
For Grade 3-4 diarrhea (or Grade 2 diarrhea that persists after initial steroid treatment),
 
 • Rule out bowel perforation. Imaging with plain films or computed tomography (CT) can be useful. • Consider consultation with gastroenterologist and confirmation biopsy with endoscopy. • Treat with intravenous (IV) steroids (methylprednisolone 125 mg) followed by high-dose oral steroids (prednisone 1-2 mg/kg once per day or dexamethasone 4 mg every 4 hours). When symptoms improve to grade 1 or less, steroid taper should be started and continued over no less than 4 weeks. Taper over 6-8 weeks in patients with diffuse and severe ulceration and/or bleeding. • If IV steroids followed by high-dose oral steroids does not reduce initial symptoms within 48-72 hours, consider treatment with infliximab at 5 mg/kg once every 2 weeks. Discontinue infliximab upon symptom relief and initiate a prolonged steroid taper over 45-60 days. If symptoms worsen during steroid reduction, initiate a retapering of steroids starting at a higher dose of 80 or 100 mg followed by a more prolonged taper and administer infliximab. CAUTION: infliximab is contraindicated in patients with bowel perforation or sepsis^b. • If symptoms persist despite the above treatment a surgical consult should be obtained. 	
peritoneal signs and ileus). In symptomatic patients, infectious etiologies should be ruled out, and if symptoms are persistent and/or severe, endoscopic evaluation should be considered.
	

Event(s)	CTCAE v5.0 Grade	Management / Next Dose for MK-3475	Action / Supportive Care Guidelines	Symptoms ^a	Differential Diagnosis
Endocrine events 
 • Hyperthyroidism • Hypophysitis • Hypopituitarism • Hypothyroidism • Thyroid disorder • Thyroiditis 	Grade 1-2	No change in dose	
 • Monitor thyroid function or other hormonal level tests and serum chemistries more frequently until returned to baseline values. 	Symptoms may include (but not limited to): 
 • Abdominal pain • Abnormal thyroid function tests and/or serum chemistries (Thyroid-stimulating hormone increased [decreased], Free thyroxine increased, Tri-iodothyronine increased.) • Arrhythmias^c • Cold or heat intolerance • Fatigue • Fever • Headache • Hypotension^c • Loss of appetite • Mental status and/or behavior changes • Nausea and/or vomiting • Unusual bowel habits • Vision disturbances • Weakness 	All attempts should be made to rule out other causes such as brain metastases, sepsis, and/or infection. An endocrinology consultation is recommended.
	Grade 3-4	Hold/discontinue MK-3475.	
 • Consider endocrine consultation. • Rule out infection and sepsis with appropriate cultures and imaging. • Treat with an initial dose of methylprednisolone 1-2 mg/kg IV followed by oral prednisone 1-2 mg/kg per day. When symptoms improve to grade 1 or less, steroid taper should be started and continued over no less than 4 weeks. Replacement of appropriate hormones may be required as the steroid dose is tapered. 		
Endocrine events 
 • Adrenal insufficiency • Hypophysitis • Pan-hypopituitarism 	Grade 1-4	Discontinue MK-3475.	
 • Thyroid hormone and/or steroid replacement therapy to manage adrenal insufficiency. • If Grade 1-2 hypophysitis is considered, pituitary gland imaging should be considered (magnetic resonance imaging [MRIs] with gadolinium and selective cuts of the pituitary can show enlargement or heterogeneity and confirm the diagnosis). • Grade 3-4 hypophysitis with clinically significant adrenal insufficiency and hypotension, dehydration, and electrolyte abnormalities (such as hyponatremia and hyperkalemia) constitutes adrenal crisis. Hospitalization and IV methylprednisolone should be initiated. 		
Eye event 
 • Uveitis 	Grade 1	Discontinue MK-3475 if symptoms persist despite treatment with topical immunosuppressive therapy	
 • Evaluation by an ophthalmologist is strongly recommended. • Treat with topical steroids such as 1% prednisolone acetate suspension and iridocyclitics. 	Symptoms may include (but not limited to): 
 • Blurred vision • Diffuse erythema and a prominent blush on the sclerae • Dryness of the eyes 	All attempts should be made to rule out other causes such as metastatic disease, infection, or other ocular

Event(s)	CTCAE v5.0 Grade	Management / Next Dose for MK-3475	Action / Supportive Care Guidelines	Symptoms ^a	Differential Diagnosis
	Grade 2	Discontinue MK-3475 if symptoms persist despite treatment with topical immunosuppressive therapy and does not improve to Grade 1 within the re-treatment period OR requires systemic treatment.	
 Evaluation by an ophthalmologist is strongly recommended. Treat with topical steroids such as 1% prednisolone acetate suspension and iridocyclitics. 	
 Pain Photophobia 	disease (e.g., glaucoma or cataracts).
	Grade 3-4	Discontinue MK-3475.	
 Treat with systemic corticosteroids such as prednisone at a dose of 1-2 mg/kg per day. When symptoms improve to ≤Grade 1, steroid taper should be started and continued over no less than 4 weeks. 		
Hepatic events 
 Hepatitis Hepatitis, Autoimmune 	Grade 1-2	No change in dose	
 Monitor liver function tests more frequently until returned to baseline values. 	Symptoms may include (but not limited to): 
 Elevations in: 
 AST >2.5 times ULN ALT >2.5 times ULN Total bilirubin >1.5 X ULN Fever Malaise Upper quadrant abdominal pain 	All attempts should be made to rule out other causes such as metastatic disease, progressive liver disease, viral hepatitis, alternative drug toxicity, infectious causes and/or myositis.
Grade 3-4	Discontinue MK-3475 when AST or ALT >5.0 times ULN and/or total bilirubin >3.0 times ULN.	
 Consider appropriate consultation and liver biopsy to establish etiology of hepatic injury, if necessary. Treat with high-dose IV glucocorticosteroids for 24-48 hours. When symptoms improve to grade 1 or less, a steroid taper with dexamethasone 4 mg every 4 hours or prednisone at 1-2 mg/kg should be started and continued over no less than 4 weeks. If serum transaminase levels do not decrease 48 hours after initiation of systemic steroids, oral mycophenolate mofetil 500 mg every 12 hours may be given. Infliximab is not recommended due to its potential for hepatotoxicity^b. Several courses of steroid tapering may be necessary as symptoms may worsen when the steroid dose is decreased 			

Event(s)	CTCAE v5.0 Grade	Management / Next Dose for MK-3475	Action / Supportive Care Guidelines	Symptoms ^a	Differential Diagnosis
Nausea	≤Grade 1	No change in dose	
 Nausea should be treated aggressively, and consideration should be given in subsequent cycles to the administration of prophylactic antiemetic therapy according to standard institutional practice. Patients should be strongly encouraged to maintain liberal oral fluid intake. 		
	Grade 2	Hold until ≤Grade 1. Resume at same dose level. May increase dosing interval by 1 week if it takes more than 4 weeks for toxicities to resolve.			
	Grade 3	Hold until <Grade 2. May increase dosing interval by 1 week for each occurrence. Discontinue if toxicities do not resolve within 12 weeks.			
	Grade 4	Off protocol therapy			
Neutropenia	≤Grade 1	No change in dose			
	Grade 2	No change in dose			
	Grade 3	No change in dose			
	Grade 4	Hold until resolves to ≤Grade 1. May increase the dosing interval by 1 week. Discontinue if toxicities do not resolve within 12 weeks.			

Event(s)	CTCAE v5.0 Grade	Management / Next Dose for MK-3475	Action / Supportive Care Guidelines	Symptoms ^a	Differential Diagnosis
Pneumonitis events 
 • Pneumonitis • Interstitial lung disease • Acute interstitial pneumonitis 	Grade 1	MK-3475 may be continued with close monitoring.	
 • Radiologic findings should be followed on serial imaging studies. • Consider pulmonary consultation and/or bronchoscopy if clinically indicated. 	Symptoms may include (but not limited to): 
 • Abnormal breath sounds • Chest pain and/or tightness^c • Dyspnea^c • Dry cough • Fatigue • Fever • Hemoptysis 	All attempts should be made to rule out other causes such as metastatic disease, bacterial or viral infection.
	Grade 2	Hold MK-3475	
To rule out other causes such as infection:
 
 • Consider pulmonary consultation with bronchoscopy and biopsy/bronchoalveolar lavage (BAL). • Consider pulmonary function tests. 
If the patient is determined to have study drug associated pneumonitis:
 
 • Treat with systemic corticosteroids at a dose of 1-2 mg/kg/day prednisone or equivalent. When symptoms improve to grade 1 or less, steroid taper should be started and continued over no less than 4 weeks. • Treatment with MK-3475 may be resumed if the event improves to ≤Grade 1 within 12 weeks and corticosteroids have been reduced to the equivalent of methylprednisolone 10 mg by mouth daily or less. Repeat chest imaging monthly as clinically indicated. 
For Grade 2 pneumonitis that improves to ≤Grade 1 within 12 weeks, the following rules should apply:
 
 • First episode of pneumonitis: May increase dosing interval by one week in subsequent cycles. • Second episode of pneumonitis: Discontinue MK-3475 if upon rechallenge the patient develops a second episode of ≥Grade 2 pneumonitis. 		

Event(s)	CTCAE v5.0 Grade	Management / Next Dose for MK-3475	Action / Supportive Care Guidelines	Symptoms ^a	Differential Diagnosis
	Grade 3-4	Discontinue MK-3475.	
 • Consider pulmonary function tests with pulmonary consult. • Bronchoscopy with biopsy and/or BAL is recommended. • Treat with IV steroids (methylprednisolone 125 mg). When symptoms improve to grade 1 or less, a high-dose oral steroid (prednisone 1-2 mg/kg once per day or dexamethasone 4 mg every 4 hours) taper should be started and continued over no less than 4 weeks. • If IV steroids followed by high-dose oral steroids does not reduce initial symptoms within 48-72 hours, treat with infliximab at 5 mg/kg once every 2 weeks. Discontinue infliximab upon symptom relief and initiate a prolonged steroid taper over 45-60 days. If symptoms worsen during steroid reduction, initiate a retapering of steroids starting at a higher dose of 80 or 100 mg followed by a more prolonged taper and administer infliximab. 		
Renal events 
 • Nephritis • Nephritis autoimmune • Renal failure • Renal failure, Acute 	Grade 1	Consider withholding MK-3475 if Grade 1 does not improve with symptomatic treatment	
 • Provide symptomatic treatment. 	Symptoms may include (but not limited to): 
 • Fatigue • High blood pressure • Increased serum creatinine • Swelling 	All attempts should be made to rule out other causes such as obstructive uropathy, progression of disease, or injury to other chemotherapy agents. A renal consultation is recommended.
	Grade 2	Consider withholding MK-3475.	
 • Systemic corticosteroids may be indicated. 		
	Grade 3-4	Discontinue MK-3475.	
 • Renal consultation with consideration of ultrasound and/or biopsy as appropriate. • Treat with systemic corticosteroids at a dose of 1-2 mg/kg prednisone or equivalent once per day. • When symptoms improve to grade 1 or less, steroid taper should be started and continued over no less than 4 weeks. • Discontinue MK-3475 if unable to reduce corticosteroid dose for irAEs to ≤10 mg. • MK-3475 treatment may be restarted and the dose modified as specified in the protocol. 		

Event(s)	CTCAE v5.0 Grade	Management / Next Dose for MK-3475	Action / Supportive Care Guidelines	Symptoms ^a	Differential Diagnosis
Skin events 
 • Dermatitis exfoliative • Erythema multiforme • Stevens-Johnson syndrome • Toxic epidermal necrolysis 
If they are considered to be immune related, ≥Grade 3 or result in dose modification or discontinuation:
 
 • Pruritus • Rash • Rash generalized • Rash maculo-papular • Vitiligo 	Grade 1-2	No change in dose	
 • Symptomatic treatment should be given such as topical glucocorticosteroids (e.g., betamethasone 0.1% cream or hydrocortisone 1%) or urea-containing creams in combination with oral antipruritics (e.g., diphenhydramine HCl or hydroxyzine HCl). • Treatment with oral steroids is at investigator discretion for grade 2 events. 		All attempts should be made to rule out other causes such as metastatic disease, infection, or allergic dermatitis.
	Grade 3	Hold MK-3475.	
 • Consider dermatology consultation and biopsy for confirmation of diagnosis. • Treatment with oral steroids is recommended, starting with 1 mg/kg prednisone or equivalent once per day or dexamethasone 4 mg four times orally daily. When symptoms improve to grade 1 or less, steroid taper should be started and continued over no less than 4 weeks. 		
	Grade 4	Permanently discontinue MK-3475.	
 • Dermatology consultation and consideration of biopsy and clinical dermatology photograph. • Initiate steroids at 1-2 mg/kg prednisone or equivalent. When symptoms improve to grade 1 or less, steroid taper should be started and continued over no less than 4 weeks. 		
Thrombocytopenia	≤Grade 1	No change in dose			
	Grade 2	No change in dose			
	Grade 3	No change in dose	
 • Grade 3 drug-related thrombocytopenia >7 days or associated with bleeding requires discontinuation. 		
	Grade 4	Hold MK-3475 until resolves to ≤Grade 1. May increase the dosing interval by 1 week.	
 • Grade 4 drug-related thrombocytopenia >7 days or associated with bleeding requires discontinuation. 		

Event(s)	CTCAE v5.0 Grade	Management / Next Dose for MK-3475	Action / Supportive Care Guidelines	Symptoms ^a	Differential Diagnosis
Vomiting	≤Grade 1	No change in dose	
 Vomiting should be treated aggressively, and consideration should be given in subsequent cycles to the administration of prophylactic antiemetic therapy according to standard institutional practice. Patients should be strongly encouraged to maintain liberal oral fluid intake. 		
	Grade 2	Hold until ≤Grade 1. Resume at same dose level. May increase dosing interval by 1 week if it takes more than 4 weeks for toxicities to resolve.			
	Grade 3	Hold until <Grade 2. May increase dosing interval by 1 week for each occurrence. Discontinue if toxicities do not resolve within 12 weeks.			
	Grade 4	Off protocol therapy			

Event(s)	CTCAE v5.0 Grade	Management / Next Dose for MK-3475	Action / Supportive Care Guidelines	Symptoms ^a	Differential Diagnosis
Other events 
 • Autoimmune neuropathy • Demyelinating polyneuropathy • Guillain-Barre • Myasthenia gravis-like syndrome • Non-infectious myocarditis • Non-infectious pericarditis • Pancreatitis • Rapid onset of grade 3 fatigue in the absence of disease progression 	Grade 1	Consider withholding MK-3475 for Grade 1 that does not improve with symptomatic treatment.	
 • Provide symptomatic treatment. 		All attempts should be made to rule out other causes. Therapeutic specialists should be consulted as appropriate.
	Grade 2	Consider withholding MK-3475.	
 • Systemic corticosteroids may be indicated. • Consider biopsy for confirmation of diagnosis. 		
	Grade 3-4	Discontinue MK-3475.	
 • Treat with systemic corticosteroids at a dose of 1-2 mg/kg prednisone or equivalent once per day. • When symptoms improve to grade 1 or less, steroid taper should be started and continued over no less than 4 weeks. • Discontinue MK-3475 if unable to reduce corticosteroid dose for irAEs to ≤10 mg. • MK-3475 treatment may be restarted and the dose modified as specified in the protocol. 		

^a The signs and symptoms may be associated with any of the diagnoses in the associated “Event(s)” column.

^b Janssen Biotech, Inc.: REMICADE (Infliximab) prescribing information revised September 2011.

http://www.accessdata.fda.gov/scripts/cder/drugsatfda/index.cfm?fuseaction=Search.Label_ApprovalHistory#labelinfo

^c If symptoms indicate possible new or worsening cardiac abnormalities, additional testing and/or a cardiology consultation should be considered

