3. PATIENT SELECTION

3.1 Eligibility Criteria

In order to be eligible for participation in this trial, the patient must:

- 3.1.1 Patients must have biopsy-proven metastatic MCC or locoregional MCC that has recurred following standard locoregional therapy with surgery and/or radiation therapy.
- 3.1.2 Patients must have measurable disease per RECIST 1.1 assessed by CT scan, or for skin lesions not measurable by CT scan, measurements may be performed with caliper or flexible ruler.

Note: Stage IV no evidence of disease (NED) is excluded by this criterion.
- 3.1.3 Be ≥ 18 years of age on day of signing informed consent

Note: Because no dosing or AE data are currently available on the use of MK-3475 in patients < 18 years of age, children are excluded from this study.
- 3.1.4 Have a performance status of ≤ 1 on the Eastern Cooperative Oncology Group (ECOG) Performance Scale (see Appendix A)
- 3.1.5 Life expectancy of greater than 6 months
- 3.1.6 Patients must have normal organ and marrow function (all screening labs should be performed within 14 days of treatment initiation) as defined below:

System	Laboratory value
- leukocytes	$\geq 2,000/\text{mcL}$
- absolute neutrophil count	$\geq 1,500/\text{mcL}$
- platelets	$\geq 100,000/\text{mcL}$
- hemoglobin	$\geq 9 \text{ g/dL}$ OR $\geq 5.6 \text{ mmol/L}$

- serum total bilirubin ≤ 1.5 X upper limit of normal (ULN) OR direct bilirubin \leq ULN for patients with total bilirubin levels >1.5 X ULN
- AST(SGOT)/ALT(SGPT) ≤ 2.5 \times institutional ULN OR ≤ 5 X ULN for patients with liver metastases
- serum creatinine ≤ 2.5 X ULN
- Measured or calculated^a creatinine clearance (CrCl) (Glomerular filtration rate [GFR] can also be used in place of creatinine or CrCl) ≥ 30 mL/min for subject with creatinine levels >2.5 X institutional ULN

OR

- Thyroid Stimulating Hormone (TSH) Within Institutional Limits (ie: Normal). If TSH is greater or less than institutional limits patients may participate if their T4 is WNL. Patients may be on a stable dose of replacement thyroid medication. Dose adjustments are allowed if needed.

^aCreatinine clearance should be calculated per institutional standard.

3.1.7 Patients must provide tissue from an archival tumor sample or newly obtained core, punch or excisional biopsy of a tumor lesion if deemed relatively safe and technically feasible.

Note: Newly obtained biopsy is preferable.

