5.4 Duration of Therapy

In the absence of treatment delays due to adverse event(s), treatment may continue for up to 2 years or until one of the following criteria applies:

- Disease progression warranting alternative systemic therapy,
- Intercurrent illness that prevents further administration of treatment,
- Patient decides to withdraw from the study.
- General or specific changes in the patient's condition render the patient unacceptable for further treatment in the judgment of the investigator.
- In patients with documented disease progression, treatment with MK-3475 can continue until one of the above occurs or until there is an increase in tumor burden of 25% or more following initial confirmation of progression.
- Unacceptable adverse event(s), including:
 - Any Grade 2 drug-related uveitis or eye pain or blurred vision that does not respond to topical therapy and does not improve to Grade 1 severity within the re-treatment period OR requires systemic treatment.
 - Grade 3 drug-related autoimmune or inflammatory event including uveitis, pneumonitis, diarrhea, colitis, neurologic adverse events, hypersensitivity reaction, or infusion reaction of any duration requires discontinuation.
 - Any Grade 3 or 4 drug-related laboratory imbalance or electrolyte abnormality, not associated with underlying organ pathology and that do not require treatment except for electrolyte replacements do not require treatment discontinuation, with the following exceptions with approval of the Principal Investigator:
 - Hypophysitis or pan-hypopituitarism any grade should discontinue treatment.
 - Grade 4 amylase or lipase abnormalities that are not associated with DM, associated liver or gall bladder inflammation clinical manifestations of pancreatitis and which decrease to <Grade 4 within 1 week of onset may stay

on study.

- Any drug-related liver function test (LFT) abnormality that meets the following criteria requires discontinuation: Grade 3 AST or ALT ($>5 \times$ ULN) and total bilirubin $>3 \times$ ULN.
- Grade 3 drug-related thrombocytopenia >7 days or associated with bleeding requires discontinuation.
- Any patient requiring systemic steroid or other immunosuppressive treatment.

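### Sections 5.4, 5.7, 6.1.1 and 6.1.2 give inconsistent stopping criteria for drug-related liver-test and Grade 4 non-hematological laboratory abnormalities, and none is said to govern

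*Combined protocol and SAP*

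**What the plan says.** **Liver tests.** Three sections set a criterion.

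- Section 5.4 lists unacceptable adverse events. One bullet begins "Any drug-related liver function test (LFT) abnormality that meets the following criteria requires discontinuation: Grade 3 AST or ALT" and joins its two limits with *and*: "ULN) and total bilirubin". AST or ALT must be above 5 x ULN and total bilirubin above 3 x ULN.
- Section 6.1.2, hepatic events, Grade 3-4: "Discontinue MK-3475 when AST or ALT >5.0 times ULN and/or total bilirubin >3.0 times ULN".
- Section 5.7 calls for permanent discontinuation when combined Grade 2 AST/ALT and total bilirubin values meet the parameters set out in Section 5.4.

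**Grade 4 laboratory values.** Two sections set a rule.

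- Section 5.4 describes "Any Grade 3 or 4 drug-related laboratory imbalance or electrolyte abnormality, not associated with underlying organ pathology" and continues "that do not require treatment except for electrolyte replacements do not require treatment discontinuation". Among the exceptions tied to Principal Investigator approval, it lets Grade 4 amylase or lipase values stay on study if they have no listed clinical association and fall below Grade 4 within a week.
- Section 6.1.1 counts laboratory abnormalities within non-hematological toxicity. Its Grade 4 row says "Subject must be discontinued".

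**Status of the sections.** Section 5.1.1 refers the reader to Section 6.1 for unacceptable adverse experiences and, later, to Section 5.4 for the discontinuation criteria. Section 6.1.2 describes its table as guidance for events judged treatment-related, with room for the physician's judgment. Section 6.1.1 calls its table general guidelines for toxicities that 6.1.2 does not list.

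**The concern.** Two sites that both follow the protocol can reach different decisions on the same laboratory result, depending on which section they consult. Section 2.2.1.2 names hepatitis among the important identified risks, so handling should be uniform.

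Stopping decisions also feed reported results. Section 13.5.3 displays the primary reason for discontinuation, and Section 13.11 summarizes exposure and dose intensity. Under the PFS sensitivity analysis in Section 13.5.1.2, a patient without documented progression or death who stops treatment is treated as progressed at the later of stopping or starting new anticancer therapy. A stop made under one section but not required under another can therefore add an event to that sensitivity analysis.

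The denominator of the response rate is not at stake. Sections 11.1.1 and 13.3.2 keep patients who stop for toxicity evaluable for response.

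**Working it through.** No sample-size or error-rate figure is involved, so the check sets the rules side by side.

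**Step 1. Liver thresholds.** Let A be AST or ALT above 5 x ULN, and B be total bilirubin above 3 x ULN. The 5.4 liver-test bullet is A and B. The 6.1.2 hepatic Grade 3-4 row is A or B.

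| Drug-related result | 5.4 liver-test bullet | 6.1.2 hepatic row |
|---|---|---|
| Neither A nor B | not required | not triggered |
| A only | not required | discontinue |
| B only | not required | discontinue |
| A and B | discontinue | discontinue |

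The rules differ in the two isolated-elevation rows.

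**Step 2. Other 5.4 bullets.** Section 5.4 also stops treatment for a Grade 3 drug-related autoimmune or inflammatory event, and it lists any patient who needs systemic steroids or other immunosuppression. The 6.1.2 hepatic Grade 3-4 row itself directs high-dose intravenous steroids. A patient diagnosed with Grade 3 hepatitis and treated as that row directs would therefore also stop under 5.4. What remains is an isolated elevation handled under the hepatic row, not classed as a Grade 3 inflammatory event and not judged to need systemic steroids. There, 5.4 says stopping is not required and 6.1.2 says discontinue.

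**Step 3. Section 5.7.** It cites the 5.4 parameters, and for AST/ALT those are Grade 3. A Grade 2 AST/ALT value cannot meet a Grade 3 limit. Read literally, the 5.7 sentence describes no patient. Read as setting its own limit, it is a third criterion.

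**Step 4. Grade 4 laboratory values.**

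| Drug-related Grade 4 value | 5.4 | 6.1.1 | Agree on permanent stopping? |
|---|---|---|---|
| Non-hematological, no organ pathology, no treatment beyond electrolytes | not required | must be discontinued | no |
| Amylase or lipase meeting the 5.4 conditions, with Principal Investigator approval | may stay on study | must be discontinued | no |
| Hematological | not required under the same exemption | hold, restart on recovery, discontinue if unresolved at 12 weeks | no direct conflict |

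The 6.1.1 table applies to toxicities that 6.1.2 does not list. Section 6.1.2 lists pancreatitis but not isolated amylase or lipase elevation, so 6.1.1 does reach the second row.

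**Step 5. Ranking.** Section 5.1.1 points to both 5.4 and 6.1. No sentence says which prevails.

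**Step 6. Scale.** The documents give no frequency for these events. If all 50 enrolled patients were dosed, one patient classified differently moves the proportion stopping for toxicity by 1/50 = 2 percentage points. That is a unit of measure and not an estimate.

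**The case against.** The best defense has four parts.

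1. *Section 6.1.2 is guidance for treatment-related events, and the row is headed hepatitis.* This stands in part. An enzyme rise not diagnosed as hepatitis can fall under 6.1.1 instead. At Grade 3 that section holds treatment, allows restart on recovery and stops only if the toxicity is unresolved at 12 weeks, which is compatible with 5.4. But guideline status does not explain why the same cut-offs carry a different connective in 5.4. Nor does it soften the mandatory wording of the Grade 4 row in 6.1.1.
2. *Section 5.4 has other bullets that would catch a true hepatitis.* This stands, and it removes the case of a frank Grade 3 hepatitis given steroids. It does not remove the asymptomatic isolated elevation described in Step 2.
3. *Section 5.4 never forbids stopping.* This stands. A site that stops under 6.1.2 does not breach 5.4. The inconsistency is between a stop that is not required and one that is directed.
4. *Enrollment is finished.* The Study Summary says the additional patients have been enrolled. Treatment can still run to 24 months, and Section 5.1.1 allows up to a further year for some patients, so the rules remain in use.

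A reader might go further and infer that all isolated elevations above these limits are decided in contrary directions, or that all Grade 4 asymptomatic laboratory values are. Points 1 to 3 and the hematological row in Step 4 rule that out. A reader might also see a clash with eligibility, because Section 3.1.6 admits AST/ALT up to "5 X ULN for patients with liver metastases". An entry limit contradicts nothing here. A later rise falls under the hepatic row only if it is judged treatment-related hepatitis, and that row asks sites first to rule out causes such as metastatic disease.

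**Conclusion.** The criteria are inconsistent as written, within limits. For liver tests, 5.4 and 6.1.2 differ for a drug-related isolated AST/ALT or isolated bilirubin elevation that is handled under the hepatic row and meets no other 5.4 stopping bullet. Section 5.7 adds a reference that does not match the section it cites. For Grade 4 non-hematological laboratory values, including certain amylase and lipase results, 5.4 and 6.1.1 differ on whether the patient must stop.

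This rests on the plain reading of the connectives and grades, and on the absence of any sentence ranking the sections. The number of patients affected is unknown. The point should be fixed because it concerns uniform handling of a named safety risk. It does not undermine the primary response analysis. No view is taken on which criterion is clinically right.

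**What to change.** Reconcile Sections 5.4, 5.7, 6.1.1 and the hepatic Grade 3-4 row of 6.1.2.

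- State one liver-test criterion, with the same connective and the same grades wherever it appears. Align the cross-reference in 5.7 with it.
- State one instruction for Grade 4 non-hematological laboratory abnormalities, naming amylase and lipase, and use it in both 5.4 and 6.1.1.
- Add a sentence saying which section governs if they differ, and how that sits with the guideline status of the Section 6 tables.

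The sponsor's clinical team decides the content of each criterion. The cost is amendment wording and a memo to sites, with no added procedures or visits. The change takes effect for patients still on treatment or retreatment. It cannot alter stopping decisions already made.
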